Objectives	
The primary objectives of the SHAReD study are:
 
 1. Does the implementation of an online shared care plan (the intervention) improve the frequency and quality of primary and preventive care received by study participants in intervention sites compared to participants in sites with usual care 3 months after their reported usual shared care ? 
The secondary objectives are:
 
 2. Does the intervention better integrate care between mental health services and general practice compared with usual care 3 months after their reported usual shared care ? 3. Does the intervention improve consumer health risks and service use compared with usual care 3 months after their reported usual shared care? 4. What are the main costs and health outcomes associated with the intervention and usual care situations, is the intervention more cost-effective compared to usual care, and are there any costs avoided (saved) 3 months after their reported usual shared care?
Study design	Pragmatic trial with the unit of randomisation being four of the five Adult Community Mental Health 'Core' Teams in Sydney Local Health District (SLHD). Pairs of teams (matched by service type and consumer population) randomised to early or late intervention 3 months after their reported usual shared care.
Planned sample size	500 consumers and their shared-care GPs
Selection criteria	
Inclusion criteria are:
 
 1. People who are clients of the SLHD Adult Community Mental Health 'Core' Teams in Canterbury, Croydon, Camperdown and Marrickville and the GPs that these consumers nominate. 2. Age: 18+ years 3. Engaged in shared care or willing to commence a shared care arrangement before participating in a baseline survey. 4. Intervention group: Has a GP engaged in shared care who consents to participate in the study and to have the electronic care plan installed. 5. Willing to provide informed consent and willingness to participate and comply with the study requirements. 
Exclusion criteria

	
Unable to give informed consent.
 
Unable to speak English or a language not supported by the study.


Study Procedure
	
 1.SLHD Adult Community Mental Health 'Core' Teams will be randomised to – 1 of Canterbury or Croydon and 1 of Camperdown or Marrickville will be randomly allocated to the intervention group and the other will receive delayed intervention 2.500 People with severe mental illness (PWSMI) who have contact with these teams and who are identified as suitable by the Core team staff member who is their care coordinator during routine visits will be given written information about the study. With the consumer’s permission, care coordinators will provide the research team with contact details of consumers who are interested in participating in the study. 3.A research officer will contact these potential participants to explain the study, answer any questions, and obtain informed consent. 4.Participant consumers will be asked to approach their GP to be part of the project OR consent to the research team doing so on their behalf to recruit GPs to the study. 5.If GPs provide consent to participate in the study, they and their patient are enrolled in the study and an appointment is made to install the INCA shared care software in the GP practice’s computer and arrangements will be made to train the GP in its use and a baseline survey is conducted with the consumers and their shared-care GPs. 6.Consumers in the intervention group will have their physical health care coordinated through an online shared care plan. 7.Consumers in the comparison group will receive usual care. 8.If GPs withdrew consent to participate in the study, their patient will remain enrolled in the study and will be able to participate in a repeat interview 3 months after their reported usual shared care. 9.Consumer and GP participants will participate in a repeat interview 3 months after their reported usual shared care. If any consumer does not have a shared care appointment/follow-up since baseline, they will be invited to participate in the repeated interview three months after 30 June 2023 (i.e., 3 months after the deadline for the intervention to be implemented). 10.With consent and approval, relevant health service use and clinical data will be extracted from medical records held by GPs, datasets held by SLHD, HealthNet (including MBS/PBS items), and the NSW Ministry of Health (ICOD). 11.A subset of consumers will be invited to participate in a qualitative interview after 3 months of their reported usual shared care. 12.A subset of SLHD mental health clinicians (Care Coordinators and shared care clinicians) and GPs will be interviewed after the intervention period.


Statistical considerations
	
Sample size calculation Assuming 20% change, a sample size of 91 per group is required to detect a change from 30 to 50% in primary outcomes based on $\alpha = 0.05$, $1-\beta = 0.8$. Assuming a design effect due to clustering of 2, a total sample of 360 is required (180 in each group).
 
Analysis plan For analysis of differences between the intervention and usual care alternatives, linear or generalised multi-level mixed models will be estimated depending on the type of outcome in question. Intra-class correlations will be calculated to compare the amount of variance associated with design features as individual participants are nested within care coordinators who are nested within community mental health teams, and those same participants are also nested within GPs who may also be nested within medical centres, which will occur before selecting random effects for these models. As well as an analysis of completers, defined as those consumers, care coordinators and GP triads that complete an online shared care plan, an intention to treat (ITT) analysis will also be completed for this study. For the ITT analysis, those who have dropped out will be treated using a variety of sensitivity analyses. Further, baseline predictors and intervention features of both the SHAReD (e-shared care) and usual care situations will be added to multi-level models to identify effects of these characteristics on outcomes. Qualitative analyses (predominantly deductive but inductive coding will also be applied to detect new and emerging themes) will also be undertaken. All relevant costs such as implementation costs and healthcare usage [hospitalisations, GP care, specialists, allied health, and prescribed medication, and the multiple outcomes such as interactions with the health system, engagement, preventive tests undertaken, clinical measures and quality of life for participants in the intervention and usual care groups will be quantified, and tests of significance will be undertaken on these data. These results will be used in a cost-consequence analysis (CCA). A comprehensive within-trial cost-effectiveness study will also be conducted provided effectiveness has been demonstrated, with the main effects/benefits consisting of satisfactory completion of an online shared care plan, reduction in consumer cardiometabolic risk, and avoiding unplanned hospitalisations. A cost-utility evaluation will be conducted if effectiveness in relation to quality of life has been demonstrated, to provide a ranking of the alternatives (e-shared care, usual care) on the basis of the amount of resources (costs) used to gain an extra quality adjusted life year (QALY) by receiving the SHAReD intervention. All the necessary effects/benefits and costs (direct medical, consumer costs for medical care and any indirect costs) will be identified, counted and valued using established methods. A range of incremental cost-effectiveness ratios (ICERs) will be calculated such as the incremental cost for an extra QALY gained, cost for an unplanned hospitalisation that was avoided. Sensitivity analysis will be conducted and some results presentations graphically.

--	---

Time Period of Data Collection	Mental health service consumers and their GPs will start to be recruited as soon as ethics approval is obtained (1 July 2021) and baseline data will be collected as soon as possible after recruitment. Recruitment and baseline data collection is expected to take 3 months. Follow-up data collection will be conducted 3 months after the consumer has had their usual shared care.
Duration of the Study	3 years
Funding (if applicable)	\$998,755
Funder	Translational Research Grants Scheme, NSW Health

Protocol Version Control box

Protocol Version Number	Date	Summary of Changes
1	25 May 2021	NA
2	2 Jul 2021	Various in response to ethics review
3	20 Jul 2021	Various in response to ethics review
4	22 March 2022	
Addition of team member approved by ethics ([name])
 
1.1 and 3 Removal of telehealth as part of the intervention – both groups will use telehealth
 
4.4 and 7 monitoring of telehealth use has been added as an indicator of integrated care.
 
4.4 3-month period removed from 2ndry outcome
 
8.2 Additional information on the economic evaluation requiring (section 7) access to additional hospital data
 
Update to start and finish dates (Table 2)
 
Removal of consumer outcome variables: Patient Activation Score, HLQ Domain and consumer travel expenses (Table 10)
 
9.4 Clarification that changes in work practice will be explored in the qualitative interviews
 
9.5 Addition of SLHD health data

5	8 July 2022	
1. Appendix 10.1 and 10.2 [name] replaced by [name], [contact] added as a contact for further information

		
 2. Appendix 10.2 Addition of reimbursement to GPs added to GP participant information 3. Appendix 10.5 Brief simple information for consumers (new) 4. Appendix 10.6 Script for explaining the participant information document to consumers (new) 5. Appendix 11.6 GP verbal consent (new) 6. Appendix 15.2 Letter to GP from consumer(new)` 7. Appendix 15.3 One-page study information for GPs (new) 8. Extension of study to 3 years noted 9. Protocol amendments: 
 i. Addition of \$100 reimbursement to GPs ii. Addition of exclusion criterion regarding language spoken by the consumer iii. Addition of GP exclusion criterion: No EMR iv. Addition of verbal consent for GPs v. Clarify how Letter to GP from consumer will be sent
6	25 Aug 2022	
 1. Appendix 3 Consumer survey 12 months changed to 9 months 2. Appendix 10.1 Consumer PIS 12 months changed to 9 months 3. Appendix 10.2 GP participant information: Change to details of reimbursement to GPs 4. Appendix 10.5 Brief information for consumers 12 months changed to 9 months 5. Appendix 15.3 One-page study information for GPs- Change to details of reimbursement 6. Protocol amendments: 
 a. Change to details of reimbursement to GPs b. 12 months changed to 9 months where applicable due to shortened follow-up period (change to 9 months already approved by ethics)
7	8 Sep 2022	
 1. Revisions to the following so consumers engage in baseline regardless of GP consent to participate in the study 
 1. Appendix 10.1 Consumer PIS 2. Appendix 10.6 Consumer PIS script 3. Protocol: flow chart

		2. Appendix 3 Consumer survey: additional questions re choice and pattern of use of GPs, some rewording to allow for multiple GPs
8	15 Dec 2022	
 1. Modification to economic evaluation 2. Addition of detail regarding the GP recruitment process, including Appendix 15.4 GP telephone recruitment & interview script 3. Revision of detail in the protocol regarding the consumer recruitment process to be consistent with the text for GP recruitment (also some recruitment details moved from 6.4 to 5.3)
9		Addition of team member: [name] (replaced [name])
10	21/07/2023	
 1. Addition of team member: [name] (Health Economic Research Officer, USYD) & [name] [name] (Research Officer, UNSW) 2. Removal of team member: [name] who leaves the project 31 August 2023 3. Appendix 3 Consumer survey: questions were deleted to avoid burden on consumers 4. Appendix 4 GP Survey: questions were modified to consider Providers in both groups (i.e., intervention and comparison) 5. Appendix 6 Consumer qualitative interview: questions were modified 6. Appendix 7 Providers qualitative interview: questions were modified to consider Providers in both groups (i.e., intervention and comparison) 7. Appendix 10.1 Consumer PIS: changes to research staff and contact for further information and to reflect changes in protocol 8. Appendix 10.2 GP PIS: Information for GPs modified to include all GPs in the follow-up phase 9. Appendix 10.3 Mental Health Service Provider PIS & 10.4 Carer PIS: changes to research staff and contact for further information 10. Appendix 12 Research Data Management Plan was modified to reflect the DTA with UNSW and USYD 11. Appendix 16. Guide to assist care coordinators informing consumers whose GPs did not consent of the implications for their participation in the study (new) 12. Appendix 17. Follow up Recruitment Advertisement (new)

		
13. Appendix 17.1a Script to call consumer for follow up survey and interview (new)
 
14. Appendix 17. 1b Script to invite consumers face-to-face to participate in follow up survey and interview (new)
 
Protocol amendments:
 
 a. 9 months changed to 3 months due to shortened follow-up period b. Changes to inclusion criteria and study procedure to include the follow-up of consumers whose GPs withdrew consent after baseline or declined after the consumer consented to the study c. Changes to study procedure to include follow-up date for consumers who did not have a shared care appointment/follow-up after baseline d. Changes to study procedure to include data extraction sources such as HealtheNet e. Changes to study procedure to include the possibility of MHS staff creating the shared care plan for GPs to review f. Health economic assessment updated to reflect changes in study protocol g. Updated Figure 1 intervention flow chart after revision with Shared Care Clinicians (MHS staff) h. Start and finish dates have been amended i. Telehealth was deleted as a secondary point j. Study flow chart updated to reflect changes to study protocol (i.e., change in the follow up timeframe) k. Changes to schedule of participant surveys and interviews to be consistent with changes in study protocol and procedure l. Changes to study visits and procedures to be consistent with changes in study protocol and procedure
11	18/10/2023	
 1. Addition of team members: [name], [name] and [name] as Research Officers, UNSW 2. Modification to the RDMP section 'Data Retention & Disposal' to reflect a) change on date for disposing of the shared data

		
with CPHCE, UNSW & University of Sydney, and b) changes on the process to confirm deletion
 
3. Modification to GP audit/HealthNet timeframe to reflect the 6-month period post-intervention, compared to 6-month pre-intervention, and same 6-month period in previous year for season effect4. Removal of outcomes to GP audit/HealthNet since they are not likely to change in reduced timeframe and have insufficient power with the reduced sample:
a. GP-recorded influenza vaccination in past 9 monthsb. Patient Absolute Cardiovascular Disease Risk scorec. GP-recorded health risk levels in past 9 months
--	--	--

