1. BACKGROUND AND INTRODUCTION

1.1. DISEASE/PROPOSED INTERVENTION BACKGROUND

The problem

People with severe mental illness (PWSMI) have a 13-30-year shorter life expectancy than the general population.¹⁻³ This is largely attributed to high rates of modifiable cardiometabolic risk factors such as smoking, hyperlipidaemia, hypertension, obesity, diet and sedentary lifestyle,^{4,5} which translates to high rates of chronic disease. As a result, PWSMI are six times more likely to die of cardiovascular disease and four times more likely to die of respiratory disease than the general public.⁶ The annual economic cost of premature comorbidity in this population necessitates better integrated care; primary care is considered ideal for managing multimorbidity.^{7,8} PWSMI have poor uptake of preventive care and proactive use of primary care due to a number of provider issues (e.g. stigma, poor communication) and consumer issues (e.g. cognitive difficulties, low health literacy).⁹ The higher mortality rate among PWSMI also requires urgent attention. The costs of treating PWSMI and premature death among people of PWSMI in Australia in 2016 was \$15 billion.¹⁰

The intervention

An online shared care plan will facilitate coordinated and planned care of consumers of mental health services “consumers” including management of risk factors and referral to allied health services and other relevant programs. It will be adapted from one used for consumers with long-term cancer patients in St George and the existing Mental Health Shared Care Checklist used in the SLHD Living Well Living Longer (LWLL program).¹¹ It will be based on the existing shared care plan used by SLHD, which is a paper form. The use of the existing shared care plan ensures the study is testing the difference between paper and online shared care plans rather than differences in the content of the plans. Functional specifications developed in consultation with mental health services (MHSs), general practitioners (GPs) and consumers in SLHD. The online shared care plan a) is interactive so the GP and MHS can review, edit and add to it (the consumer can view it); b) generates automated reminders for GPs, care coordinators and consumers; and c) enables MHSs to monitor completion and evaluate outcomes. The MHS care coordinators and peer support workers will assist the consumers and any nominated carers to access the INCA software and review their plans.

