4.5. SITES

Site Name/s	The study site is Sydney LHD. Teams involved in the study will be four adult Community Mental Health 'Core' Teams at Canterbury, Croydon, Camperdown and Marrickville
Site Contact/Investigator	[name]
PHO	YES
If a non-PHO is an EEA in place?	N.A.
Study Procedures	
Procedures have been developed in consultation with site team leaders and staff and will be the consistent across all four mental health teams. The number of active consumers with each team varies from 278 to 448. It is anticipated that each team will recruit approximately one-quarter of the total sample, with larger teams recruiting slightly more than smaller sites.
 
Care coordinators at each team will identify and approach potential study participants. They will be given written information to give to the consumer. With the consumer’s permission, care coordinators will provide the research team with contact details of consumers who are interested in participating in the study.
 
A research officer will contact these potential participants to explain the study, answer any questions, and obtain informed consent. In intervention sites, participant consumers will be asked to approach their GP to be part of the project or consent to the research team doing so on their behalf to recruit GPs to the study.
 
For consumers in the intervention group, if GPs provide consent to participate in the study, they and their patient are enrolled in the study and an appointment is made to install the shared care software in the practice’s computer and arrangements will be made to train the GP in its use.
 
Consumers in the comparison group will receive usual care. If their GP decline to be involved in the study, these consumers will remain enrolled in the study for intention-to-treat analysis.
 
Consumer participants will participate in a baseline survey which is repeated 3 months after their usual shared care appointment, or 3 months after 30 June for those consumers who did not attend their shared care appointment. These interviews will be conducted via telephone, online or face-to-face, depending upon the preference of each consumer.
 
All consumers will be invited to participate in a qualitative interview after the 3-month survey.
 
Care Coordinators and GPs will also be interviewed after the intervention period.

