Secondary data from GP records, and SLHD eMR data (including hospitalisations, ED visits and ambulatory care records, associated costs, documentation audit report and metabolic report) as well as information from SLHD Targeted Activity & Reporting System (STARS) will be obtained and merged with the consumer survey data within the SLHD by AI [name]/AI [name]. GP records will be used to answer research questions 1 and 2 – quantitative analysis is described above. SLHD's patient data from the eMR (including hospitalisation, ED visits, ambulatory data, documentation audit and metabolic monitoring) as well as information from STARS and cost information will be used to answer research questions 3 and 4. These analyses of the resulting combined and de-identified dataset are described below.

The merged SLHD administrative data (micro-level data) will be from a 6-month period post-intervention (May-October 2023, considering the intervention as having a shared care plan in Inca between May and June 2023) compared with the 6-month periods, a) pre-intervention (November 2022-April 2023) and b) in the previous year (May-October 2022, to check for seasonal effect). The data will be analysed as part of the healthcare cost component (in the larger health economic evaluation).

The healthcare usage (such as hospitalisations, ED visits, ambulatory care and GP care) data will firstly be grouped in a meaningful way e.g., for hospitalisations, summarised by ARDRGs, diagnoses and average length of stay. Costs will be summarised too e.g., for hospitalisation costs, these will be described in terms of main components such as 'Medical', 'Nursing' and 'Allied Health' costs occurring during admissions. We will calculate the total and mean utilisation of healthcare services and costs (and undertake further econometric analyses) for those in the SHAReD intervention, usual care, and combined (SHAReD and comparison) groups. These summary statistics (and later modelled estimates) will be included in the cost component of the economic evaluation.

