14. LIST OF APPENDICES

- 1. SLHD Data from the Integrated Care Outcomes Database (ICOD)**
- 2. MBS and PBS data (specific items)**
- 3. Consumer survey questionnaire**
- 4. Provider (GP) questionnaire**
- 5. Recruitment advertisement**
- 6. Consumer qualitative interview guide**
- 7. Providers qualitative interview guide**
- 8. Consumer invitation letter**
- 9. Consumer expression of interest form**
- 10. Participant information sheets:**
 - 10.1. Information for consumers**
 - 10.2. Information for GPs**
 - 10.3. Information for Mental Health Service providers**
 - 10.4. Information for carers**
 - 10.5. Brief information for consumers (separate versions for a) intervention and b) control groups)**
 - 10.6. Script for explaining study information to consumers**
- 11. Consent forms:**
 - 11.1. Written consent form for consumers**
 - 11.2. Verbal consent form for consumers**
 - 11.3. Consent form for GPs**
 - 11.4. Consent form for Mental Health Service providers**
 - 11.5. Consent form for carers**
 - 11.6. Verbal consent form for GPs**
- 12. Data management plan**
- 13. Letter of invitation to care coordinators**
- 14. ED Presentations, hospitalisation and medical treatment data using medical record numbers from the SLHD Performance Unit**
- 15. GP recruitment**
 - 15.1. GP invitation letter from Mental Health Service**
 - 15.2. GP invitation letter from consumer**
 - 15.3. Brief information for GPs**

- 15.4. GP telephone recruitment & interview script**
- 16. Guide to assist care coordinators informing consumers whose GPs did not consent of the implications for their participation in the study**
- 17. Follow-up Recruitment Advertisement**
 - 17.1a Script to call consumer for follow up survey and interview**
 - 17.1b Script to invite consumers face-to-face to participate in follow up survey and interview**

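### Team allocation is listed before consumers are chosen, consented and surveyed, and the planned baseline adjustment does not protect against selection by arm

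*Protocol*

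**What the plan says.** The Study Procedure in the protocol synopsis is a numbered sequence. Item 1 is the draw: one team of each pair "will be randomly allocated to the intervention group and the other will receive delayed intervention". In item 2, consumers are "identified as suitable by the Core team staff member who is their care coordinator during routine visits". Consent follows in item 3, the GP approach in item 4, and GP consent, the software appointment and the baseline survey in item 5. The synopsis row on the time period of data collection agrees that "baseline data will be collected as soon as possible after recruitment".

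Section 4.5 gives selection to the same staff: "Care coordinators at each team will identify and approach potential study participants". Section 1.1 also gives them a part in the intervention: "The MHS care coordinators and peer support workers will assist the consumers and any nominated carers to access the INCA software". Section 6.2 has the care coordinator review and adjust the plan.

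Several recruitment elements depend on the arm:
- Section 14, Appendix 10.5: "Brief information for consumers (separate versions for a) intervention and b) control groups".
- Section 4.5: "In intervention sites, participant consumers will be asked to approach their GP to be part of the project".
- Section 5.3 (recruitment of GPs): different retention of declining GPs' details by arm.
- Section 5.3, item 11: software installation now for the intervention group and later for the comparison group.

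The stated safeguards are an independent coin toss (4.1), procedures described as consistent across the four teams (4.5), and adjustment for baseline differences (5.4 and 8.2).

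**The concern.** In a cluster trial, randomising teams makes the teams comparable by design. It makes the enrolled individuals comparable only if they are fixed, or chosen without regard to arm, before the arm is known. Here the people who judge suitability work in the allocated team and support the online plan. A coordinator in an intervention team may, without intending it, favour consumers who engage with care. Such consumers are also plausibly more likely to be screened, advised and prescribed for, which is what the primary outcomes measure. Willingness to consent can also differ once the consumer knows what the team offers.

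An independent coin toss does not address this, because it protects the allocation of teams and not the choice of people within them. Section 5.5 does not list the issue as a limitation.

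**Working it through.** **1. Order of steps.** The numbered procedure puts the draw first. Section 4.1 describes how the coin is tossed but not when. The arm-specific brief sheet and the intervention-site GP step cannot be used as written unless the arm is known. The inference that recruitment followed allocation is therefore strong, but it remains an inference.

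**2. Is the baseline contaminated by treatment?** Table 2 dates recruitment 03/2022 to 12/2022. Section 8.2 defines the intervention as "having a shared care plan in Inca between May and June 2023". The baseline survey and both GP-record comparison periods in Table 9 (May-October 2022 and November 2022-April 2023) precede the online plans. They are post-allocation on the reading above, but pre-treatment, so they are usable as covariates.

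**3. The planned effect, as a yardstick.** For 30% v 50%, two-sided alpha 0.05 and power 0.80: (1.960 + 0.842)² × (0.3×0.7 + 0.5×0.5) / 0.2² = 90.26, rounded up to 91 per group, as stated. A design effect of 2 gives 182 per group and 364 in total, against the stated 180 and 360. The sample size is not affected by this point. An effective sample is 180 / 2 = 90 per arm.

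**4. How a difference in mix acts.** Let q be the share of engaged consumers in an arm, and let a and b be the outcome rates in engaged and other consumers, with no intervention effect.
- Level after the intervention: the arms differ by (q_I − q_C) × (a − b).
- Change from the pre-period: if a and b are constant over time, each arm's change is zero, so the arms differ by zero.
- If the rate among engaged consumers would have risen by δ more than among the others, the change comparison is biased by (q_I − q_C) × δ.

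None of these quantities is in the documents. As pure assumption, mix differences of 10 to 30 points and rate differences of 20 to 40 points give level gaps from 0.10 × 0.20 = 2 points to 0.30 × 0.40 = 12 points. With 90 effective per arm and a 30% base rate, a nominal 5% test of levels would then reject a true null about 6% to 39% of the time. The same inputs give no bias in change. This shows the mechanism and is not an estimate for this trial.

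**5. Which comparison is planned?** Section 4.4 defines the primary endpoints as differences between groups in changes. Section 8.2 says only that outcomes after the intervention will be compared in mixed models. It does not say that the pre-period value of the outcome enters the model.

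**6. What the significance rule would catch.** A difference in a binary baseline characteristic reaches 5% significance at about 1.96 × √(2p(1−p)/n).
- n = 90: 1.96 × √(2×0.21/90) = 13.4 points at p = 0.3; 1.96 × √(2×0.25/90) = 14.6 points at p = 0.5.
- n = 180, clustering ignored: 9.5 and 10.3 points.

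Smaller observed imbalances would go unadjusted even if measured. Neither 5.4 nor 8.2 names engagement as a variable to be measured for this purpose.

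**7. Room for selection.** Four teams of 278 to 448 active consumers hold between 278 + 448 + 2×278 = 1,282 and 278 + 448 + 2×448 = 1,622 people. Criterion 3 of section 5.1 restricts entry to those in shared care or willing to start. Section 1.1 counts 736 active shared-care consumers in the programme, and 500 / 736 = 68%. That count is not limited to the four teams and leaves out willing newcomers, so the eligible pool is not known.

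**The case against.** The strongest reply is that the primary endpoints are changes. Two of the three primary outcomes in Table 9 come from GP records, with two pre-intervention periods as reference. Stable differences between recruits then largely cancel. This stands, and it limits the point considerably. What remains is a possible difference in trend between the kinds of people recruited, and the fact that 8.2 does not commit the model to the pre-period value.

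Safeguards also exist. Section 6.4 ties screening to the study criteria, waiting-room advertisements invite consumers to come forward, and 8.2 adjusts beyond the variables in 5.4. These reduce the scope for selection. They do not require that all eligible consumers, or a random sample of them, be approached.

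Some of the arm-specific evidence is weaker than it looks. The synopsis (item 4) and the GP recruitment part of 5.3 describe the GP approach without restricting it to one arm. That step also overlaps with the separate question of GP consent as an intervention-arm criterion. Selection by coordinators would remain if that criterion were removed.

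Stronger readings that a reader might infer are not supported:
- *The draw is documented as preceding recruitment.* No section dates it.
- *All consumer information differs by arm.* Only the brief sheet is listed in two versions; the full sheet (10.1) and the script (10.6) are listed once. The brief sheet was added in version 5 (8 July 2022), after the 03/2022 recruitment start in Table 2, and its text is not shown.
- *The bias can be sized against the 20-point effect.* That needs invented rates and a comparison of levels.
- *Only 31% to 39% of the pool is recruited (500/1,622 to 500/1,282).* That denominator ignores the shared-care criterion.

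**Conclusion.** The point holds as a design weakness and a gap in the analysis. The listed order, together with the arm-specific recruitment elements, implies that unblinded coordinators who support the intervention chose whom to approach. Adjusting for age, sex and whatever tests significant at baseline does not protect against that. The direction and size cannot be derived from the documents. A comparison of post-intervention levels is exposed. The change comparison of section 4.4 is largely protected if engaged and other consumers would have followed similar trends.

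A reader might infer that consumers consented after the draw should be left out of the primary comparison. The documents do not support this: on the listed order that is every participant, so the exclusion would empty the trial. The conclusion rests on the numbered list being the actual order, which the sponsor can confirm from the date of the toss.

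**What to change.** **Design.** Reorder items 1 to 5 so that consumers in all four teams are identified, consented and surveyed with one common information sheet before the coin is tossed, with software installation starting after the draw. Replace the two versions of Appendix 10.5 with one, and align sections 4.5 and 5.3. The cost is later installation and GP training. Table 2 and section 8.2 leave January to April 2023 between the end of recruitment and the first online plans, though the documents do not show that four months would have sufficed. Version 11 is dated 18/10/2023, after recruitment on Table 2's dates, so this part can serve only consumers not yet recruited.

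**Analysis of participants already recruited after the draw.** Keep them in the primary comparison. In 8.2, replace the significance-test rule with adjustment, in every primary model, for:
- the baseline or pre-period value of the outcome: the baseline survey for consumer-reported advice or referral, and GP records for November 2022-April 2023 and May-October 2022 for screening and prescribing;
- prior shared-care and GP engagement, defined in advance. Pre-period GP visits and the shared-care status reports in Table 9 are candidate sources.

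This needs a protocol amendment and a definition of engagement, using data already planned. It reduces the bias but cannot remove selection on what is not measured.

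**Reporting.** State the date of the coin toss relative to first consent. Report numbers eligible, approached and consented by team. Add post-allocation recruitment to the limitations in 5.5.
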